1. BACKGROUND AND RATIONALE

This Protocol describes an open-label study, to evaluate the anti-tumoral activity of erlotinib (Tarceva®) through objective response rate (ORR) in patients with non-small-cell lung cancer (NSCLC) in locally advanced or metastatic stages who have not received previous chemotherapy for their disease and who present activating mutations in the tyrosine kinase (TK) domain of the epidermal growth factor receptor (EGFR).

1.1 Background

Non-small cell lung cancer is the most common cause of cancer death worldwide¹. In the EU the crude incidence of lung Cancer is 52.5 patients per 100,000 individuals each year with a mortality rate of 48.7 per 100,000/year. Mortality and incidence rates are very similar, due to low survival of these patients². In the developed world lung cancer remains the commonest reason of cancer death in both men and women, although mortality rates for men are dropping³. Among men the incidence and mortality rates are 82.5 and 77.0 per 100,000/year, respectively, and for women these rates are 23.9 and 22.3 per 100,000/year, respectively.

Non-small cell lung cancer (NSCLC) comprises 80% of reported lung cancer cases and the majority of its new cases are diagnosed in an advanced stage^{4,5} once it represents a disease for which there is no established screening. Survival statistics are among the worst for any malignancies, and have not improved in the last years⁶. Indeed, nowadays the median survival for lung cancer is 6–12 months from the time of diagnosis with an overall 5-year survival of 5–10%.

Nowadays surgery (lobectomy/pneumonectomy plus mediastinal lymph node dissection) offers the best chance of cure in lung cancer, especially for NSCLC cases. However, only a small part of patients are suitable for curative resection and the majority must rely on non-surgical and adjuvant therapies. For most patients resection was technically unsuitable because of obvious dissemination of disease. Therefore, chemotherapy with palliate purpose to prolong patients' life for few months has been increasingly proved by clinical studies. A common first-line therapy for advanced cases of NSCLC in patients with good performance status (PS) is based on combinations of platinum. Despite the first-line chemotherapy is appropriate, most patients experience disease progression. With regard to second-line systemic treatment (docetaxel, pemetrexed, erlotinib) this may improve the symptoms related to disease and survival of patients. Second-line therapy is administered for disease progression, recurrence, or intolerable adverse effects following administration of initial chemotherapy⁷.

In first line, doublet chemotherapy has been found to be superior to single-agent chemotherapy⁸. Platinum-based chemotherapy combined with vinorelbine, gemcitabine or a taxane prolongs survival, improves quality of life and controls symptoms in patients with

good performance status. Non-platinum combination chemotherapy can be considered in patients who are not fit to receive platinum agents.

In Second line, in a phase III study, Shepherd and colleagues proved the efficacy of erlotinib against placebo in increasing the survival and reduced symptoms⁹. Erlotinib response rates are higher in non-smokers, women, adenocarcinomas, Asians and patients with EGFR mutations. Several studies show that erlotinib prolongs survival in patients with advanced NSCLC after the failure of first line or second line chemotherapy.

In a phase II clinical trial, 57 patients with refractory NSCLC received erlotinib monotherapy and showed a response rate of 12.3% and a median survival of 8.4 months¹⁰. Based on these results and for a different pharmacological profile, erlotinib was approved by the FDA for the treatment of second and third line NSCLC. Some studies have also shown that mutations in the EGFR gene are associated with response to EGFR TKI¹¹.

1.2 Study drug

Erlotinib (OSI-774; Tarceva[®])

Erlotinib is an orally active and potent inhibitor of tyrosine kinase, which acts on the epidermal growth factor receptor (EGFR) developed for the treatment of solid tumours including NSCLC¹². The recommended daily dose of erlotinib is 150 mg¹³.

Erlotinib acts via direct and reversible inhibition of the human EGFR tyrosine kinase, with an IC₅₀ of 2 nM (0.786 ng/mL) in an in vitro enzyme assay, and reduces receptor autophosphorylation in intact tumour cells with an IC₅₀ of 20 nM (7.86 ng/mL).

At nanomolar concentrations, erlotinib blocks Epidermal Growth Factor (EGF)-dependent cellular proliferation and inhibits cell cycle progression in the G1 phase. Selectivity testing against a panel of isolated tyrosine kinase demonstrated that erlotinib is selective for the EGFR.

The most frequently-reported adverse events (AEs) associated with single-agent erlotinib are rash (dermatosis), diarrhoea, nausea, fatigue, stomatitis, vomiting, and headache. On the other hand, skin rash was identified as a key indicator of erlotinib trough plasma concentrations¹⁴. These results support those from previous studies on EGFR inhibitors, which have revealed a similar association between drug steady-state plasma concentrations and the intensity of rash and diarrhoea^{15,16}. Laboratory abnormalities, primarily involving changes in liver function tests (elevation of alanine aminotransferase (ALT), aspartate aminotransferase (AST), and/or bilirubin) are less frequently observed with single-agent erlotinib. These abnormalities occur occasionally in patients treated with erlotinib in combination with either gemcitabine, or carboplatin and paclitaxel. Caution should be used when administering Tarceva to patients with hepatic impairment. Dose reduction or interruption of Tarceva should be considered if severe adverse reactions occur^{13,17}.

An indication of completed and ongoing clinical studies on erlotinib in NSCLC can be found in the Investigator's Brochure.

1.3 Rationale for the Study

Advanced NSCLC remains largely fatal, with the positive impact of chemotherapy limited by intrinsic and acquired resistance, manifested clinically by early progression and transient responses. Current chemotherapy regimens have limited efficacy with a magnitude of

survival benefit that is still modest, and lead to significant toxicity, with many patients unable to tolerate this kind of treatment, even in the first-line setting. There is, therefore, a great need to provide patients with less toxic agents such as the novel targeted therapies, with the potential to improve the efficacy and maintain a good quality of life with little associated toxicity.

In order to improve upon the doublet chemotherapy platform for NSCLC, the targeted drugs were next tested in the frontline setting in large, randomized, phase III trials in unselected population were added TKIs to chemotherapy (trials with erlotinib TRIBUTE¹⁸ and TALENT¹⁹). Those trials failed to demonstrate either an improved response or a survival benefit from the combination of a TKI with chemotherapy in unselected population with advanced NSCLC. Despite the failure of the first-line trials, additional phase III trials were completed to confirm the previously observed activity in refractory NSCLC. The BR.21 trial randomized patients previously treated with chemotherapy to erlotinib or placebo, and showed a significant improvement in response rate (9% vs 1%) and overall survival (OS; 6.7 vs 4.7 months; $P < 0.001$) with erlotinib.

Subsequently, a number of trials have confirmed the benefit of erlotinib in unselected patients with NSCLC. As example, in the SATURN study erlotinib has proven results as first-line maintenance therapy following non-progression of disease after first-line therapy²⁰. The SATURN trial investigated erlotinib maintenance therapy in patients with advanced NSCLC who did not progress during first-line chemotherapy. This randomized, global, phase III study was the first to include prospective molecular marker analyses for erlotinib, with mandatory sample collection.

Nowadays it is accepted the important role of erlotinib in NSCLC tumors with EGFR mutations after at least one prior chemotherapy regimen (SATURN study)²¹. Therefore it is important to define the impact that treatment with erlotinib may have in the first line setting. There is some clinical trial evidence that EGFR TKIs are efficacious as first-line therapy in EGFR mutation positive patients with advanced NSCLC: IPASS is a phase III trial looking at gefitinib as a first-line treatment in non-small cell lung cancer in 1217 patients (261 EGFR mutation positive). Exploratory analysis of response rates in patients with EGFR mutations have shown a response rate of 71.2% in patients with EGFR mutations treated with gefitinib versus a response rate of 1.1% in patients without EGFR mutations treated with gefitinib²².

Therefore, erlotinib is currently being assessed as first-line treatment in advanced NSCLC in prospective, randomized, registration trials. There is however, already evidence that erlotinib works in first-line treatment with relevant results found for the evaluation of PFS. Paz-Ares²³ performed a pooled analysis of clinical outcomes in patients with EGFR mutations, treated with either an EGFR TKI or chemotherapy and demonstrated clinical efficacy of erlotinib (and gefitinib) monotherapy in 1st line NSCLC.

Table 1 - Summary of data included in pooled analysis

	Erlotinib	Gefitinib	Chemotherapy
Patients treated in any line, n	365	1069	375

Patients treated in first-line setting, %	57	57	95
---	----	----	----

Table 2 - Pooled analysis of outcomes according to line of therapy

	Pooled median PFS, months (95% accuracy interval)		
	Erlotinib	Gefitinib	Chemotherapy
Any line	13.2	9.8	5.9
	(12.0-14.7)	(9.2-10.4)	(5.3-6.5)
First-line	12.5	9.9	6.0
	(10.0-16.0)	(9.0-10.9)	(5.4-6.7)

The results of this pooled analysis are consistent with those from other studies looking at EGFR TKIs as first-line therapy in patients with EGFR mutations such as the IPASS study of first-line gefitinib versus carboplatin/paclitaxel in Asian patients with adenocarcinoma who were never- or light ex-smokers where the median PFS was found to be 9.5 months with gefitinib and 6.3 months with chemotherapy; and the Spanish Lung Cancer Group study of erlotinib in patients with EGFR mutations showed a medium PFS of 14.0 months and an ORR (complete and partial response) of 70.6%²⁴. These results highlight the idea that EGFR mutants lung cancer is a distinct class of NSCLC.

A recent phase III study (OPTIMAL) of first line treatment with erlotinib compared to platinum-based chemotherapy (gemcitabine/carboplatine), in Asian population with NSCLC with EGFR mutation has shown a median PFS of 13.1 months in the erlotinib arm with HR=0.16 (95% CI; 0.10-0.26) versus 4.6 months in the chemotherapy arm. It has also shown an ORR of 82.9% in the erlotinib arm versus 36% in the chemotherapy arm (p<0.0001)²⁵. Erlotinib should therefore be considered in preference to first line chemotherapy in patients with this distinct disease.

Considering the potential benefit for patients in initiating erlotinib earlier in their treatment it becomes crucial to evaluate its anti-tumoral activity through a more sensitive and accurate endpoint such as objective response rate during first-line treatment in Caucasian populations.

In this trial erlotinib will be given in first-line treatment for advanced NSCLC with EGFR mutation positive.

Although this trial is a non-randomized phase II trial, Erlotinib is currently used in clinical practice to treat NSCLC²⁶. Any patient with locally advanced or metastatic non-small cell lung cancer disease found to have an EGFR exon 19 deletion or exon 21 mutations will be offered first-line treatment with erlotinib having ORR as primary efficacy endpoint.

EGFR mutations rates in Portugal

Previous studies with gefitinib have shown the incidence of mutations to be around 8% in unselected patients, whereas studies conducted in Asia show mutation rates of 19-60% In the Spanish Lung Cancer Group study of erlotinib that included only Spanish patients with EGFR mutations the EGFR mutation rate was 16.6%. In this trial, the population was mainly female, non-smokers and adenocarcinoma. The EGFR mutation's rate amongst

NSCLC patients, in Portugal is currently unknown so that the health burden and economic implications of treatments directed specifically at patients with this characteristic cannot be accurately assessed.

Therefore one of the objectives of the current study is to assess the EGFR mutation rate in Portugal NSCLC population. This will be done by testing Portuguese patients newly diagnosed with recurrent or metastatic NSCLC for the EGFR mutations.

2. OBJECTIVES

2.1 Primary Objectives

To evaluate the anti-tumoral activity of erlotinib (Tarceva[®]; 150 mg) through objective response rate (ORR) in patients with non-small-cell lung cancer (NSCLC) in locally advanced or metastatic stages who have not received previous chemotherapy for their disease and who present activating mutations in the tyrosine kinase (TK) domain of the epidermal growth factor receptor (EGFR).

2.2 Secondary Objectives

To evaluate progression-free survival (PFS), defined as the time from baseline visit to the date of first occurrence of disease progression or death due to any cause.

To evaluate the EGFR mutation frequency, in the study population.

To evaluate the Overall Survival defined as the time from baseline visit to the date of death due to any cause.

To evaluate the erlotinib safety profile (Tarceva[®]; 150 mg).

To evaluate response duration (RD) defined as the time of initial response (CR/PR whichever is first recorded) until documented disease progression.

[figure not shown]
3. STUDY DESIGN

3.1 Overview of Study Design

This is a local open-label, multi-centre Phase II study of the anti-tumoral activity of erlotinib (Tarceva[®]; 150 mg) evaluated by objective response rate (ORR) in patients with NSCLC in locally advanced or metastatic stages who have not received previous chemotherapy for their disease and who present activating mutations in the TK domain of the EGFR.

Summary of the study design is shown in Figure 1.

Figure 1 - Summary of study design

Rationale for Study Design

In this trial erlotinib is given in first-line treatment for advanced NSCLC.

Although this trial is non-randomized phase II trial, as Erlotinib is currently used in clinical practice to treat NSCLC it closely reflects clinical practice.

Any patient with locally advanced or metastatic non-small cell lung cancer disease found to have an EGFR Exon 19 deletion or exon 21 substitution L858R in the TK domain of EGFR gene will be offered first-line treatment with erlotinib.

The primary efficacy variable will be ORR.

Rationale for Dose Selection

The recommended daily dose of erlotinib was established at 150 mg, to be continued daily until disease progression.

All enrolled patients will receive recommended dose of erlotinib (150 mg/day). No dose escalation is permitted. Erlotinib dose will be reduced for toxicities as detailed in Section 6.1. Patients will be treated until progression of disease or unacceptable toxicity.

End of Study

This study is event-driven, with a recruitment period that will last until the end of March 2012 or until the number of patients aimed for the protocol (30) is achieved, whatever occurs first. Patients are to be treated until disease progression, unacceptable toxicity or patient request for discontinuation.

The study will end when the last patient has stopped erlotinib therapy and completed their last safety follow-up visit (28 days after last study drug administration). For all patients who have discontinued study drug treatment and are alive, information on survival will be collected.

3.2 Centres

This study will comprise approximately 9 centres, in Portugal.

3.3 Interim Analyses

One interim analysis is planned for the study. This interim analysis will include an epidemiological, efficacy and safety characterization of erlotinib in 1st line EGFR Mut+ mNSCLC Portuguese population. The rationale for this interim analysis is to analyse the preliminary clinical benefits on this population and compare it with the available data in publications held in the caucasian international population.

Additionally, the interim analysis will evaluate the EGFR mutation rate; describe the enrolled population related to the gender, histology type, smoking habit and the incidence of EGFR mutation per sub-group; as well as the safety evaluations in terms of events, frequency and severity.

4. Materials and methods

Under no circumstances subjects who are enrolled in this study are not permitted to be re-enrolled for a second course of treatment with erlotinib in this study.

4.1 Overview

The target population of this study are patients with histologically or cytologically confirmed locally advanced or metastatic NSCLC who have not received previous chemotherapy for their disease and who present activating mutations in the TK domain of the EGFR.

4.2 Inclusion Criteria

A subject may be included if the answer to all of the following statements is "yes".

1. Patients able and willing to give written informed consent. Consent must be obtained prior to any study-specific procedure.
2.
 - a) Histologically or cytologically documented inoperable, locally advanced or metastatic NSCLC disease;
 - b) Patient that presents activating mutations (exon 19 deletion and/or exon 21 substitution L858R) in the tyrosine kinase domain of EGFR ;
3. Measurable disease, according to RECIST - *Response Evaluation Criteria in Solid Tumours*).
4. Male or female patients aged ≥ 18 years.
5. Life expectancy ≥ 12 weeks.
6. Adequate haematological and coagulation function as assessed by the investigator.
7. Adequate liver and renal function as assessed by the investigator.
8. Female patients must be postmenopausal (24 months of amenorrhea), surgically sterile or they must agree to use a physical method of contraception. Male patients must be surgically sterile or agree to use a barrier method of contraception. Male and female patients must use effective contraception during the study and for a period of 90 days following the last administration of erlotinib. Acceptable methods of contraception include an established hormonal therapy or intrauterine device for females, and the use of a barrier contraceptive (i.e. diaphragm or condoms) with spermicidal.
9. If applicable, patients with asymptomatic and stable cerebral metastases receiving medical treatment will be eligible for the study. Those patients may have received radiation therapy for their cerebral metastases before the initiation of systemic treatment for non-small-cell lung cancer.

10. Able to comply with the required protocol and follow-up procedures.

4.3 Exclusion Criteria

A subject will be excluded if the answer to any of the following statements is "yes".

1. Previous treatment with chemotherapy or therapy against EGFR, either with antibody or small molecule (tyrosine kinase inhibitor) for metastatic disease. The administration of neo-adjuvant or adjuvant therapy is allowed as long as it has finalized • 6 months before entering the study. Patients can have received radiotherapy as long as the irradiated lesion is not the only target lesion for evaluating response and as long as radiotherapy has been completed before initiating the study treatment (28 days period is recommended). Treatment with an investigational drug agent during the four weeks before enrolment in the study.
2. History of another neoplasm other than carcinoma in situ of the uterine cervix, basal cell skin carcinoma treated adequately, or prostate carcinoma with a good prognosis (Gleason • 6) treated radically. History of another neoplasm treated curatively and without evidence of disease in the last 5 years. History of breast cancer and melanoma at any time.
3. Patients with symptomatic cerebral metastases.
4. Known hypersensitivity to erlotinib or any of its excipients.
5. Any significant ophthalmologic abnormality, especially severe dry eye syndrome, keratoconjunctivitis sicca, Sjögren's syndrome, severe exposure keratitis or any other disorder likely to increase the risk of corneal epithelial lesions. (The use of contact lenses is not recommended during the study. The decision to continue to wear contact lenses should be discussed with the patient's treating oncologist and the ophthalmologist.)
6. Use of coumarins (Sintrom[®]; Varfine[®]). If the patient requires anti-coagulant therapy, instead of coumarins, the use of a low molecular weight heparin is recommended, whenever clinically possible.
7. Patients with severe hepatic and renal impairment as assessed by the investigator.
8. Evidence of any other disease, neurological or metabolic dysfunction, physical examination or laboratory finding giving reasonable suspicion of a disease or condition that contraindicates the use of an investigational drug or puts the patient at high risk for treatment-related complications.
9.
 - a) Positive urine/blood pregnancy test in women of childbearing potential.
Female patients should not be pregnant or breast-feeding.

- b) Patients (male or female) with reproductive potential not willing to use effective method of contraception during the trial and during 90 days after the last erlotinib administration. Oral or injectable contraceptive agents cannot be the sole method of contraception.
10. Patients with pre-existing disease of the lung parenchyma such as lung fibrosis, lymphangitic carcinomatosis.
 11. Patients with known infection with HIV, HBV, HCV. Testing is not required in the absence of clinical signs and symptoms suggestive of these conditions.
 12. Patients those in the Investigator's opinion are not able to accomplish protocol requirements.
 13. Incapacity to take oral medication or previous surgical procedures that affect absorption and imply the need for intravenous or parenteral feeding.

4.4 Number of Subjects/ Assignment to Treatment Groups

Approximately 30 patients will be recruited over a planned recruitment period that will last until the end of March 2012 or until the number of patients aimed for the protocol is achieved, whatever occurs first.

4.5 Concomitant Medication and Treatment

All concomitant medications and blood products administered to patients after the first dose of study drug, until 28 days after the last dose of study drug must be recorded on the electronic case report form (eCRF).

Permitted medication and therapies:

- Patients may receive non-myelosuppressive palliative radiation therapy if required. Concomitant radiation therapy with erlotinib treatment is allowed.
- Patients will receive full supportive care throughout the study, including transfusion of blood products, treatment with antibiotics, anti-emetics, anti-diarrheals, and analgesics as appropriate.
- Patients exhibiting dry eyes should be advised to use an ocular lubricant.

Not permitted:

- Administration of any other anti-cancer therapy (cytotoxic or biological/immunotherapy) is not permitted until after disease progression has been documented.
- Patients who have received study drug should not receive any other investigational drugs until after the post-treatment assessment (at least 28 days after the final dose of study drug).

Caution should be exercised when erlotinib is co-administered with CYP3A4 inhibitors and inducers. As grapefruit juice has the potential to inhibit CYP3A4 activity, patients should not eat grapefruit or drink grapefruit juice during the study.

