If the positive FDG-PET at follow-up corresponds to a pre-existing site of disease on CT that is not progressing on the basis of the anatomic images, this is not PD.

4. Evaluation of best overall response

The best overall response is the best response recorded from the start of the study treatment until the end of treatment taking into account any requirement for confirmation. On occasion a response may not be documented until after the end of therapy so protocols should be clear if post-treatment assessments are to be considered in determination of best overall response. Protocols must specify how any new therapy introduced before progression will affect best

response designation. The patient's best overall response assignment will depend on the findings of both target and non-target disease and will also take into consideration the appearance of new lesions. Furthermore, depending on the nature of the study and the protocol requirements, it may also require confirmatory measurement. Specifically, in non-randomized trials where response is the primary endpoint, confirmation of PR or CR is needed to deem either one the 'best overall response'. This is described further below.

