#### 5.3.9.1 Primary Efficacy Endpoint

The primary efficacy endpoint is the objective response rate (ORR) defined by the number of patients with complete response (CR) or partial response (PR) as the best overall response during the treatment period divided by the total number of patients based on diagnostic imaging according to RECIST 1.1 (see Appendix 5). The ninety five percent (95%) confidence interval will be estimated for the ORR.

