## **5.4 MISSING DATA**

Incomplete dates will be handled as stated in Appendix 4. All other missing values will be individually omitted from the analyses.

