### Treatment period

**Response duration:** It will be measured from the time of initial response (CR/PR whichever is first recorded) until documented tumor progression (in weeks).

**Best overall response:** a categorical variable will be obtained, defined as the best response across all time points, according to RECIST 1.1, until end of study treatment. The following criteria will be considered:

Complete response – Patients who presented at least one complete response;

Partial response – Patients who not presented a complete response and presented at least one partial response;

Stable disease – Patients who not presented response (complete or partial) and presented at least one stable disease;

Progression disease – Patients who not presented response or stable disease and presented progression disease;

Inevaluable – All assessments are inevaluable.

**Objective response:** A dichotomous variable (yes/no) will be calculated. Patients who presented complete response or partial response as the best overall response will be classified in “yes”. Otherwise patients will be classified in “no”.

**Event PFS:** A dichotomous variable (yes/no) will be calculated. Patients who presented progression disease or death for any cause will be classified in “yes”. Otherwise patients will be classified in “no”.

**Time PFS:** Time between baseline visit and date of first occurrence of disease progression or death for any cause (in weeks) while the patient was under study or during the prolonged follow-up period. In patients where disease progression or death from any cause was not observed, the time will be censored at the date of last visit or last contact with the patient.

**Time overall survival:** The time from the first dose of erlotinib (assumed to be baseline visit) to the date of death due to any cause (in weeks). For patients alive at the end of the follow-up period, the time was censored at the date of last visit or last contact with the patient.

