### **4. Evaluation of best overall response**

The best overall response is the best response recorded from the start of the study treatment until the end of treatment taking into account any requirement for confirmation. On occasion a response may not be documented until after the end of therapy so protocols should be clear if post-treatment

assessments are to be considered in determination of best overall response. Protocols must specify how any new therapy introduced before progression will affect best response designation. The patient's best overall response assignment will depend on the findings of both target and non-target disease and will also take into consideration the appearance of new lesions. Furthermore, depending on the nature of the study and the protocol requirements, it may also require confirmatory measurement. Specifically, in non-randomized trials where response is the primary endpoint, confirmation of PR or CR is needed to deem either one the 'best overall response'. This is described further below.

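### Does palliative radiotherapy given during erlotinib need its own rule in the response analysis?

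*Protocol*

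**What the plan says.** Protocol 4.5 lists radiotherapy among the permitted treatments: "Patients may receive non-myelosuppressive palliative radiation therapy if required. Concomitant radiation therapy with erlotinib treatment is allowed". It does not restrict it to non-target lesions. The same section bars other treatment: "Administration of any other anti-cancer therapy (cytotoxic or biological/immunotherapy) is not permitted until after disease progression has been documented". The parenthesis does not name radiotherapy, so irradiation before progression complies with the protocol.

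SAP Appendix 3 classes a patient as a partial responder as follows: "Patients who not presented a complete response and presented at least one partial response". All time points up to the end of study treatment count. SAP 5.3.9.1 carries this into the primary ORR, taking CR or PR "as the best overall response during the treatment period divided by the total number of patients". Response duration starts at the same event: "It will be measured from the time of initial response (CR/PR whichever is first recorded) until documented tumor progression".

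The RECIST text in Protocol Appendix 1 and SAP Appendix 5, section 4 on best overall response, contains this instruction: "Protocols must specify how any new therapy introduced before progression will affect best response designation".

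Radiotherapy is linked to target lesions in two other places, and both concern the situation before treatment. Exclusion criterion 1 does not let a lesion irradiated before study be the only target. RECIST section 1.3 says that lesions in a previously irradiated area are usually not measurable at baseline, and leaves the conditions to the protocol.

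**The concern.** The trial has one arm and its primary endpoint is tumour shrinkage. PR is a fall of at least 30% in the sum of target diameters, so shrinkage of an irradiated target enters that sum directly. If that shrinkage takes the sum past the threshold, the patient is reported as an erlotinib responder, and response duration starts from that scan.

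No other provision removes such a patient. The missing-data rule in SAP 5.4, "All other missing values will be individually omitted from the analyses", does not apply, because the scan exists. Permitted radiotherapy is not among the listed deviations, so the per-protocol set keeps the patient. Protocol 8.1.3 provides no independent review. Counting these responses can only raise the ORR or leave it unchanged. The documents also reproduce a RECIST instruction that they appear not to follow.

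**Working it through.** **The plan's own figure.** Protocol 8.2.6 and SAP 5.1 give N = 30 and a margin of about ±17.5% for a 95% interval. The normal-approximation half-width is 1.96 × √(p(1−p)/30). At p = 0.60 it is 17.5 points and at p = 0.50 it is 17.9. The stated margin reproduces and does not depend on how radiotherapy is handled.

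**Effect per patient.** One reclassified patient moves the ORR by 1/30 = 3.3 points, and 3.3/17.5 = 0.19, about one fifth of the planned margin. For illustration, assume 21 of 30 respond, close to the 70.6% that Protocol 1.3 cites for a Spanish study of erlotinib. The documents give no expected number of patients irradiated on study, so the range 0 to 3 is also an assumption. Intervals are exact binomial (Clopper-Pearson).

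| Responses set aside | ORR | 95% CI |
|---|---|---|
| 0 | 21/30 = 70.0% | 50.6–85.3 |
| 1 | 20/30 = 66.7% | 47.2–82.7 |
| 2 | 19/30 = 63.3% | 43.9–80.1 |
| 3 | 18/30 = 60.0% | 40.6–77.3 |

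**When irradiation can produce a PR.** Let s be the irradiated lesion's share of the baseline sum and d the proportional shrinkage of the other targets (d < 0.30). The sum falls by 30% when the irradiated lesion shrinks by (0.30 − (1−s)d)/s. Setting this to 1 (complete disappearance) gives the smallest share that can tip the result: s = (0.30 − d)/(1 − d).

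| d | Smallest share s | Shrinkage needed, two equal targets (s = 0.50) |
|---|---|---|
| 0 | 30.0% | 60% |
| 0.15 | 17.6% | 45% |
| 0.20 | 12.5% | 40% |
| 0.25 | 6.7% | 35% |

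The table has two implications. If the other targets have not responded, only a lesion with a large share of the tumour burden can produce a PR. If they have nearly reached 30%, a small lesion can tip the result, but most of the shrinkage then lies outside the irradiated field and calling the PR a radiotherapy effect is doubtful. The cases that tip easily are the ones hardest to attribute to radiotherapy.

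**How often it could arise.** Protocol 5.3 asks for an unscheduled tumour assessment when progression is suspected, and treatment runs only until progression. A patient whose symptoms prompt palliative irradiation may therefore be scanned first and leave with PD. Irradiating non-target disease, such as blastic bone lesions (non-measurable under RECIST 1.3), does not change the target sum. Under the RECIST time-point table, new lesions or non-target PD override a target PR.

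**What the plan yields as written.** Protocol 4.5 permits the treatment and Appendix 3 takes the best response over all time points without exception. Together they give one result: the response counts as observed. Two analysts following the text would get the same ORR.

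**What an added rule would yield.** An obvious candidate is a supportive ORR in which time points after irradiation of a target are inevaluable unless PD.
- It would turn a genuine responder who was irradiated before the first documented response into a non-responder, even if the irradiated lesion was too small to matter.
- RECIST section 4.2 takes a different approach to incomplete lesion data. It asks whether the individual lesion would change the time-point response.
- Radiotherapy to a non-target lesion might avert a PD that would have overridden a later PR, and the rule would miss this. The result would not be a clean lower bound.
- It needs the site and date of each course. Protocol 4.5 requires recording of concomitant medications and blood products without naming radiotherapy, and SAP Listing 3 is a medication listing with no site column.

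**The case for a change.** The strongest argument for acting is that the RECIST sentence is an instruction, both documents reproduce it, and neither answers it for the one tumour-directed treatment that Protocol 4.5 expressly permits before progression. The baseline rules show that the sponsor recognised the problem of irradiated targets and dealt with only half of it. Protocol 3.3 intends the interim results to be compared with published data, so an inflated ORR would have an audience. Three patients would be 10 points (70.0 − 60.0), against the 82.9 − 70.6 = 12.3 points that separate two erlotinib response rates cited in Protocol 1.3. If the site of radiotherapy is not recorded, the question may be hard to settle afterwards.

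Much of this stands. The omission is genuine and its direction is known. Two parts are weaker. Whether radiotherapy already permitted as concomitant care is new therapy in the RECIST sense is a matter of reading. The data are also less exposed than they look: Protocol 14.1 counts hospital records and imaging reports among the source documents, and SAP Table 9 summarises lesion location. With 30 patients, a case could probably be traced if it arose, although the documents do not guarantee this.

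**Conclusion.** No change to the plan follows. What is missing is a written policy for a case that may never occur. The rule as written still gives a single, reproducible primary ORR. The effect is 3.3 points per affected patient, upward or nil, on a descriptive estimate whose 95% interval is roughly ±17 points. Protocol 8.2.2 has no hypothesis test, so no conclusion can be reversed. An extra sensitivity analysis would rest on one convention among several, would not bound the effect cleanly, and would depend on data not shown to be collected. If a target lesion is irradiated before a first response, the analyst can say so in the report and give the count.

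This rests on three assumptions: few patients have a target lesion irradiated before their first documented response (0 to 3 is assumed, not derived), 21/30 is only illustrative, and the ORR remains an estimate without a decision rule. If radiotherapy to targets proved common, or if the ORR were tested against a threshold, the point would deserve another look.
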